- Preclinical studies have shown that combined treatment of trametinib plus HCQ elicited striking tumor regression in animal model.

Objective:

- To determine whether the 5-month progression free survival (PFS) of the trametinib plus hydroxychloroquine (HCQ) combination in subjects with refractory bile tract carcinoma (BTC) with KRAS mutation exceeds 25%.

Eligibility:

- Histopathological confirmation of BTC or carcinoma highly suggestive of a diagnosis of BTC
- Tumor must have KRAS mutation.
- Patients must have disease that is not amenable to potentially curative resection, transplantation or ablation.
- Age ≥ 18 years
- Patients must have measurable lesion by RECIST 1.1.

Abbreviated Title: Trametinib and HCQ in BTC

Version Date: 04/06/2022

- At least two weeks washout period from previous therapy
- ECOG ≤ 2
- Adequate renal, hepatic and bone marrow function

Design:

- The study is open-labeled phase 2 study. It is designed to enroll total 30 patients with refractory BTC, to test the hypothesis that treatment with a combination of HCQ and trametinib prevents cancer progression/recurrence. We propose that this combination will have relative safety profile and antitumor efficacy in BTC patients with KRAS mutation.

TABLE OF CONTENTS

PRÉCIS.....	2
TABLE OF CONTENTS	4
STATEMENT OF COMPLIANCE	9
1 INTRODUCTION	9
1.1 Study Objectives.....	9
1.1.1 Primary Objective:.....	9
1.1.2 Secondary Objectives:	9
1.1.3 Exploratory Objectives:.....	9
1.2 Background and Rationale.....	10
1.2.1 Bile tract carcinoma and KRAS mutation	10
1.2.2 Challenge of targeting mutant KRAS.....	10
1.2.3 Autophagy.....	11
1.2.4 Rationale for combining inhibitors of MEK and Autophagy	13
1.2.5 Trametinib.....	14
1.2.6 Hydroxychloroquine	18
1.2.7 Drug dose rationale	20
2 ELIGIBILITY ASSESSMENT AND ENROLLMENT	20
2.1 Eligibility Criteria.....	20
2.1.1 Inclusion Criteria	20
2.1.2 Exclusion Criteria	22
2.1.3 Recruitment Strategies.....	23
2.2 Screening Evaluation	23
2.2.1 Screening activities performed prior to obtaining informed consent	23
2.2.2 Screening activities performed after a consent for screening has been signed.....	24
2.3 Participant Registration and Status Update Procedures.....	25
2.3.1 Screen Failures.....	25
2.3.2 Treatment Assignment Procedures (for registration purposes only):	25
2.4 Baseline Evaluation	25
3 STUDY IMPLEMENTATION	26
3.1 Study Design.....	26
3.1.1 Dose Limiting Toxicity (DLT) (Safety Run-In only).....	27
3.1.2 Safety Run-In:.....	28

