1 INTRODUCTION

1.1 Study Objectives

1.1.1 Primary Objective:

- To determine whether the 5-month PFS of the trametinib plus hydroxychloroquine (HCQ) combination in subjects with refractory bile tract carcinoma (BTC) with KRAS mutation exceeds 25%.

1.1.2 Secondary Objectives:

- To determine the safety, tolerability and feasibility of the trametinib plus HCQ combination in subjects with refractory BTC with KRAS mutation.
- To evaluate the response rate (RR) (CR+PR) in patients with refractory BTC with KRAS mutation treated with the combination of trametinib plus HCQ
- To access overall survival (OS).

1.1.3 Exploratory Objectives:

- To evaluate the bioactivity of the combination of trametinib plus HCQ against the MEK1/2 and autophagy pathways.
- To measure changes in immune parameters in the peripheral blood and tumors of patients with refractory KRAS mutation BTC treated with the combination of trametinib plus HCQ.
- To explore mechanism of primary and secondary resistance to the combination of trametinib plus HCQ in patients with refractory KRAS mutation BTC.
- To evaluate the relationship between the RR, OS and immune parameters, in patients with refractory KRAS mutation BTC treated with the combination of trametinib plus HCQ.

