3 STUDY IMPLEMENTATION

3.1 Study Design

The proposed study is an open label, single-arm phase II study of trametinib in combination with hydroxychloroquine (HCQ) in BTC patients (**Schema 1**).

Initially, 6 patients will be enrolled into safety run-in portion of the trial (section **3.1.2**). If safe, we will continue enrollment as planned, if not, we will submit next amendment with new study design.

Initially, 10 patients will be enrolled and evaluated for progression. Enrollment will be temporarily halted after the 10th patient has been accrued, unless we know that 3 patients have passed the 5-month point without progression. If 3 or more of the first 10 patients enrolled have not progressed at the 5-month evaluation, then accrual will continue until a total of 17 patients have been entered. If, among the first 10 patients accrued, 0 to 2 are able to be progression-free at the 5-month evaluation, then no further patients will be enrolled after such a determination has been made. If 6 or more of the total cohort of 17 patients have been found to be progression-free at 5 months, then this will indicate an adequate progression free probability to justify further consideration of trametinib in combination with hydroxychloroquine in this population of patients. On the other hand, if 3 to 5 of 17 are progression-free at 5 months, this will be considered insufficient.

Treatment with trametinib and HCQ will be delivered in cycles consisting of 4 weeks (+/- 3 days) and start on cycle 1 day 1.

Both drugs will be given orally on daily basis: trametinib (2 mg once a day) and HCQ (600 mg twice a day – 1,200 mg total dose).

[figure not shown]
Treatment with study drugs will continue until off treatment criteria are met (see section **3.6.1**).

If one of the study drugs is permanently discontinued because of toxicity, per PI discretion the patient may continue the other study drug. It is unclear in terms of the attitude and duration of antitumor efficacy with this drug combination in BTC. If patient's disease is controlled with the combination but the treatment is held because of AEs from one of the agents, we think it would be beneficial for participants to continue the other agent and continue monitoring the disease progress accordingly.

Patients will be monitored every 8 (+/- 1) weeks with imaging studies.

Patients will be evaluated for toxicity and malignancy per Study Calendar **3.4**.

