10.2 Sample Size Determination

The primary objective of this study is to determine in a preliminary, limited size trial whether trametinib in combination with HCQ is associated with a 5-month progression free probability, which exceeds 25% when used to treat patients with cholangiocarcinoma.

Based on our analysis of data from previous trials of patients with similar eligibility requirements the median progression free survival in BTC is 2.5 months[8]. This translates to 25% without progressive disease at 5 months following an exponential failure model. Based on these results, it would be useful to demonstrate whether trametinib in combination with hydroxychloroquine is able to be associated with a median PFS of 5 months, which would correspond to 50% of patients having stable disease at 5 months. The trial will be conducted using a two-stage optimal design [52]. In order to attempt to determine if the agent offers any improvement, using alpha=0.10 and beta =0.10 as acceptable error probabilities, the trial will target 50% as the desirable proportion of patients who are still without progression at the five-month evaluation ($p_1=0.50$), and will be considered inadequate if only a fraction consistent with 20% are without progression by the same evaluation time ($p_0=0.20$).

Initially, 10 patients will be enrolled and evaluated for progression. Enrollment will be temporarily halted after the 10th patient has been accrued, unless we know that 3 patients have passed the 5-month point without progression. If 3 or more of the first 10 patients enrolled have not progressed at the 5-month evaluation, then accrual will continue until a total of 17 patients have been entered. If, among the first 10 patients accrued, 0 to 2 are able to be progression-free at the 5-month evaluation, then no further patients will be enrolled after such a determination has been made. If 6 or more of the total cohort of 17 patients have been found to be progression-free at 5 months, then this will indicate an adequate progression free probability to justify further consideration of trametinib in combination with hydroxychloroquine in this population of patients. On the other hand, if 3 to 5 of 17 are progression-free at 5 months, this will be considered insufficient. Under the null hypothesis (20% progression free at 5 months), the probability of being able to stop accrual after 10 patients have been evaluated at 5 months is 68%.

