In addition to evaluation of the proportion of patients that are progression-free at 5 months, the progression-free survival for patients will also be analyzed via a Kaplan-Meier curve. This curve will be compared informally to other published results in similar patients. As well, the overall response rate will be reported, and the overall survival will be reported using a Kaplan-Meier curve. It is anticipated that up to 10 patients per year will be able to enroll onto this protocol. Thus, it is expected that accrual of up to 17 total patients can be completed in approximately 2 years. In order to allow for a small number of unevaluable patients and screen failures, the accrual ceiling will be set at 30 patients.

To evaluate the response rate, proportion of patients obtaining CR and PR per RECIST 1.1 criteria of all evaluable patients will be analyzed.

To address safety, tolerability and feasibility of trametinib in combination with hydroxychloroquine, adverse events will be tabulated by grade according to CTCAE and analyzed and reported descriptively. The fraction of patients who experience a response will be reported along with confidence intervals.

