10.4.2 Analysis of the Primary Endpoints

The fraction of patients who are able to not have progressive disease at 5 months will be reported along with a 95% confidence interval. A Kaplan-Meier curve of PFS will also be created and reported along with the 5-month PFS probability and its 95% confidence interval.

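### The primary objective asks whether 5-month PFS exceeds 25%, but the two-stage rule is built on an unexplained 20% null and declares success 21% of the time when the true rate is 25%

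*Combined protocol and SAP*

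**What the plan says.** The objective appears four times with the same threshold. The précis asks whether 5-month PFS "in subjects with refractory bile tract carcinoma (BTC) with KRAS mutation exceeds 25" per cent. Sections 1.1.1 and 10.1.1 repeat it, the latter under the heading for the statistical hypothesis, and 10.2 opens with it again.

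Section 10.2 then explains where 25% comes from. It takes a historical median PFS of 2.5 months and says: "This translates to 25% without progressive disease at 5 months following an exponential failure model". The hoped-for median is 5 months, which gives 50%.

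A few lines later the design parameters are alpha = 0.10, beta = 0.10, p1 = 0.50 and p0 = 0.20. The regimen "will be considered inadequate if only a fraction consistent with 20% are without progression by the same evaluation time". The only early-stopping figure, 68%, is tied to that value: "Under the null hypothesis (20% progression free at 5 months), the probability of being able to stop accrual after 10 patients".

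The decision rule is the same in 3.1 and 10.2. Accrual stops if 0 to 2 of the first 10 patients are progression-free at 5 months; otherwise it continues to 17. Success is defined as follows: "If 6 or more of the total cohort of 17 patients have been found to be progression-free at 5 months".

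Section 10.4.2 specifies estimation rather than a test: "The fraction of patients who are able to not have progressive disease at 5 months will be reported along with a 95% confidence interval".

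**The concern.** The threshold in the objective and the null in the design are different numbers, and nothing links them. The 25% is the protocol's own estimate of what comparable patients achieve already, so a regimen at 25% offers no improvement, and 10.2 says the purpose is to find out whether there is any. Setting the null at 20% makes the rule easier to pass than the stated question requires. The error rate quoted for the rule then says nothing about that question.

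Two things are at stake. A regimen that only matches the benchmark could be carried forward more often than a reader of 10.2 would believe. And a result at the cut-off, 6 of 17, could be reported as meeting the primary objective although it does not show that the rate exceeds 25%.

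**Working it through.** **Inputs**, all from 10.2 (the rule is repeated in 3.1): n1 = 10, stop if 2 or fewer; N = 17, success if 6 or more; p0 = 0.20; p1 = 0.50; alpha = beta = 0.10, with alpha one-sided as this type of design implies; historical median 2.5 months; stated early-stop probability 68%.

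**Formulas.** With X ~ Bin(10, p) in stage 1 and Y ~ Bin(7, p) in stage 2:

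- Early stop: P(X ≤ 2).
- Success: Σ over x = 3 to 10 of P(X = x) · P(Y ≥ 6 − x).

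**Step 1: the benchmark.** 0.5^(5/2.5) = 0.25. The derivation of 25% is correct.

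**Step 2: the plan's own figures at p = 0.20.** Early stop = 0.1074 + 0.2684 + 0.3020 = 0.678, which reproduces the stated 68%. Success = 0.094, within 0.10. At p = 0.50, success = 0.904, so power is at least 0.90. A full search confirms that this is the optimal two-stage design for 20% versus 50%.

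**Step 3: the same rule at p = 0.25.** Early stop = 0.0563 + 0.1877 + 0.2816 = 0.526. Success is built up as follows:

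| x of 10 | P(X = x) | P(Y ≥ 6 − x) | product |
|---|---|---|---|
| 3 | 0.2503 | 0.2436 | 0.0610 |
| 4 | 0.1460 | 0.5551 | 0.0810 |
| 5 | 0.0584 | 0.8665 | 0.0506 |
| 6 or more | 0.0197 | 1 | 0.0197 |
| Total | | | 0.212 |

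**Summary**

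| True 5-month rate | Early stop | Success |
|---|---|---|
| 20% | 0.678 | 0.094 |
| 25% | 0.526 | 0.212 |
| 50% | 0.055 | 0.904 |

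**Step 4: how far the alpha reaches.** Setting the success probability to 0.10 and solving for p gives p = 0.203. The rule keeps its 10% error only for nulls up to 20.3%.

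**Step 5: what results at and just above the cut-off show.** At 6 of 17 the exact one-sided 90% lower bound is 19.7% and the exact 95% interval is 14.2% to 61.7%. At 7 of 17 the lower bound is 24.6%, and a rule requiring at least 7 of 17 would have error 0.103 at a true rate of 25%. So neither 6 nor 7 of 17 shows a rate above 25% at the 10% level. These bounds treat the 17 patients as a single-stage sample. Steps 2 to 4 use the two-stage rule, which is why 19.7% and 20.3% differ slightly.

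**Step 6: what a 20% null implies.** Under the same exponential model, median = 5 · ln 2 / (−ln 0.20) = 2.15 months, against the 2.5 months cited.

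**The case against.** The strongest reply is that p0 in a two-stage screening design is the rate judged inadequate and need not equal the historical rate. Rates between 20% and 50% can be left as a zone of indifference, in which case 0.212 at 25% is one point on the operating characteristic curve and not a breached alpha. The protocol labels 20% as its null and never claims an error of 0.10 at 25%. It also calls the trial preliminary, and success only justifies further consideration. The interval planned in 10.4.2 would show at 6 of 17 that 25% is not excluded.

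Part of this stands. A p0 below the benchmark is a legitimate choice, the arithmetic for it is right, and the planned interval limits the harm at the reporting stage. But the documents never state an indifference zone, and that reading conflicts with an objective that says four times that 25% must be exceeded. The go/no-go decision is a count and not an interval, and 10.4.2 contains no test against 25%. If an error of 0.21 at the benchmark is acceptable, the protocol has to say so, because the only acceptable figure it names is 0.10. Section 1.2.1 links KRAS mutation to poor prognosis, which might motivate a lower null, but the protocol does not make that argument and keeps 25% for the KRAS-mutant population.

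**Conclusion.** The concern holds. The decision rule is sound for 20% versus 50% but does not test the stated primary objective. At the protocol's own 25% benchmark the chance of declaring success is 0.212, about twice the stated alpha, and the chance of stopping after 10 patients is 53%, not 68%. Neither figure is in the document. It must be fixed, because it concerns the primary hypothesis and the error rate of the trial's decision.

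The calculation assumes independent patients, all with known status at 5 months, and strict use of the rule. The 25% is taken from 10.2 as it stands; the source behind the 2.5-month median was not examined.

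**What to change.** Make one of two text changes. They can be combined, and the rule in 3.1 and 10.2 stays the same under both.

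1. **Restate the objective.** Change the threshold to 20% in the précis, 1.1.1, 10.1.1 and the opening of 10.2, and give the reason for a null below the 25% historical rate, noting that 20% implies a median of about 2.15 months. This is the change that removes the contradiction. It costs four wording edits and a justification.

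2. **Keep the objective and disclose.** Add to 10.2: *The design tests 20% versus 50%. If the true rate equals the 25% historical benchmark, the rule has a one-sided type I error of about 0.21 and an early-stop probability of about 53%. A result of 6 or 7 of 17 will not be reported as showing that the rate exceeds 25% at the 10% level.* This costs three sentences and a less favourable published error rate. The two thresholds remain, but the conclusion is limited to what the design supports.

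Changing the design is not required. A cut-off of 7 of 17 gives error 0.103 at 25% and power 0.823, missing both 10% limits. Meeting both limits at 25% versus 50% takes 26 patients (minimax) or 27 (optimal). That is 9 or 10 more, about one further year at the stated 10 per year. It would leave 30 − 26 = 4 or 30 − 27 = 3 places under the ceiling for unevaluable patients and screen failures, against 30 − 17 = 13 now.

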10.3 Population for Analysis

Any patient who receives at least one dose of both agents will be included in the efficacy evaluations.

Any patients who receive at least one dose of either agent will be included in the safety evaluations.

10.4 Statistical analysis

10.4.1 General approach

The fraction of patients who do not have progressive disease by 5 months will be reported.

10.4.2 Analysis of the Primary Endpoints

The fraction of patients who are able to not have progressive disease at 5 months will be reported along with a 95% confidence interval. A Kaplan-Meier curve of PFS will also be created and reported along with the 5-month PFS probability and its 95% confidence interval.

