10.4.3 Analysis of the Secondary Endpoint

The safety of the treatment will be monitored, and any toxicities identified will be reported by type and grade. The feasibility and tolerability will be assessed and reported descriptively.

In each cohort, the fraction of patients who experience a response (PR + CR) will be reported along with 80% and 95% two-sided confidence intervals.

Overall survival will be calculated from the on-study date using the Kaplan-Meier method.

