10.4.6 Planned Interim Analyses

There are no planned interim analyses for efficacy.

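### Does the primary 5-month fraction need a named interval method, an allowance for the stage-1 stop, and an 80% level to match the alpha of 0.10?

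*Combined protocol and SAP*

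**What the plan says.** Section 10.2 sets the design: "The trial will be conducted using a two-stage optimal design", "using alpha=0.10 and beta =0.10 as acceptable error probabilities", with null rate 20% and target rate 50%. The decision is a count at each stage. Section 3.1 gives the first: "If 3 or more of the first 10 patients enrolled have not progressed at the 5-month evaluation", accrual goes on to 17. Section 10.2 gives the second: "If 6 or more of the total cohort of 17 patients have been found to be progression-free at 5 months", the combination merits further study. No confidence interval enters either step.

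Section 10.4.2 covers estimation: "The fraction of patients who are able to not have progressive disease at 5 months will be reported along with a 95% confidence interval". It adds a Kaplan-Meier estimate of 5-month PFS, also with a 95% interval. It names no interval method and no other level. Section 10.4.3 says the response rate "will be reported along with 80% and 95% two-sided confidence intervals". Section 10.4.6 states "There are no planned interim analyses for efficacy". Nothing in section 10.4 says how the primary interval treats the stage-1 stop.

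**The concern.** The primary endpoint is tested at 10%. The count rule is one-sided by construction, so the matching interval is a two-sided 80% one, with 10% in each tail. The plan gives that level to the response rate, which has no test, and not to the endpoint that has one. A reader could therefore see a trial declared positive at 6/17 beside a 95% interval that contains the 20% null.

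The missing method adds to this. At 7/17 the ordinary exact 95% interval contains 20% and the Wilson interval does not, and both comply with section 10.4.2. A single-stage interval also ignores that accrual could have stopped at 10, which in principle disturbs coverage. At stake is whether the published interval could mislead, or be chosen after the data are seen.

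**Working it through.** **Inputs (sections 3.1 and 10.2).** Stage 1: 10 patients, stop at 0-2 progression-free. Final: 17 patients, pass at 6 or more. Null rate 0.20, target 0.50. All figures assume 10 then 7 evaluable patients unless stated.

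**Reproducing the design.** Let X be the stage-1 count out of 10 and Y the count among the next 7.

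- P(stop at stage 1 | 0.20) = P(X ≤ 2) = 0.678; section 10.2 states 68%.
- P(pass | p) = Σ over x = 3 to 10 of P(X = x) · P(Y ≥ 6 − x).
- At p = 0.20: x = 3 gives 0.2013 × 0.1480 = 0.0298; x = 4 gives 0.0881 × 0.4233 = 0.0373; x = 5 gives 0.0264 × 0.7903 = 0.0209; x ≥ 6 gives 0.0064. The total, before rounding, is 0.0943, within alpha 0.10.
- At p = 0.50 the same sum is 0.9040, so beta is within 0.10.
- Without the stage-1 stop, P(S ≥ 6 of 17 | 0.20) = 0.1057. The stop is for futility only, so it lowers the type I error.

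**Intervals.** With γ = 0.025 (95%) or 0.10 (80%):

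- Ordinary exact: the lower limit solves P(S ≥ s) = γ and the upper solves P(S ≤ s) = γ, with S binomial on 17.
- Wilson: [p̂ + z²/2n ± z√(p̂(1−p̂)/n + z²/4n²)] / (1 + z²/n).
- Two-stage (stage-wise ordering): put Q(s, p) = Σ over x = 3 to 10 of P(X = x)·P(Y ≥ s − x); the lower limit solves Q(s, p) = γ and the upper solves 1 − Q(s+1, p) = γ.

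| Result | Rule | 95% exact | 95% Wilson | 95% two-stage | 80% exact | 80% Wilson | 80% two-stage |
|---|---|---|---|---|---|---|---|
| 4/17 | fail | 6.8-49.9 | 9.6-47.3 | 8.4-56.3 | 10.7-41.6 | 13.1-38.7 | 13.3-46.5 |
| 5/17 | fail | 10.3-56.0 | 13.3-53.1 | 11.2-58.5 | 15.1-47.8 | 17.6-44.9 | 16.4-49.7 |
| 6/17 | pass | 14.2-61.7 | 17.3-58.7 | 14.6-62.4 | 19.7-53.7 | 22.3-50.8 | 20.3-54.3 |
| 7/17 | pass | 18.4-67.1 | 21.6-64.0 | 18.6-67.2 | 24.6-59.4 | 27.3-56.6 | 24.8-59.6 |
| 8/17 | pass | 23.0-72.2 | 26.2-69.0 | 23.0-72.2 | 29.7-65.0 | 32.5-62.1 | 29.8-65.0 |

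(All in percent.)

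**Size of the stop's effect on the 95% exact limits.** At 6/17 the limits move by 14.6 − 14.2 = 0.4 and 62.4 − 61.7 = 0.7 point; at 7/17 by under 0.2; from 8/17 by under 0.1.

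**Coverage of the ordinary exact 95% interval under the two-stage design.** Add the probabilities of all outcomes whose interval contains p. Over true rates 0.20 to 0.50 in steps of 0.001 the minimum is 95.6%, at 0.50. There the interval misses at 0 or 1 of 10 (11/1024 = 0.0107), at 3 or 4 of 17 (0.0089) and at 13 or more of 17 (3214/131072 = 0.0245). The sum is 0.0442 before rounding, and 1 − 0.0442 = 0.956. At 0.20 coverage is 98.9%. It falls below 95% only at true rates of 0.560-0.565, where the minimum is 93.9%.

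**Does an 80% interval at the cut call for a two-stage method?** At 6/17 the ordinary exact interval contains 20% (19.7%) and the two-stage one does not (20.3%). But the Wilson interval, which also ignores the stop, excludes 20% at 6/17 (22.3%) and contains it at 5/17 (17.6%). Agreement with the rule is therefore not special to the two-stage method. Nor is it assured: with 10 then 8 patients, the two-stage 80% lower limit at 6/18 is 19.4%. Such a denominator is possible, because section 10.3 counts everyone who receives both agents and section 10.2 says "In order to allow for a small number of unevaluable patients and screen failures, the accrual ceiling will be set at 30 patients".

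**The case for a change.** The best case for a change is that it costs two or three sentences and removes a choice made after the data are known. Results at the cut are not rare: exactly 6/17 makes up 9% of passes at a true rate of 50%, 23% at 40% and 31% at 35%. The method can alter the reading elsewhere too. At 4/17 the upper 95% limit is 49.9% by the ordinary exact method and 56.3% by the two-stage one, so only the first excludes the 50% target. Some unadjusted intervals also undercover: the Wilson 80% interval covers only about 70% at a true rate of 40%, and by the same enumeration the Wilson 95% interval falls to 91.2% at a true rate of 0.413.

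This stands as a reason for the analyst to choose an exact method. It does not show that the plan gives a wrong answer. A 95% interval containing a null rejected at one-sided 10% is a difference of level, and no section promises that the two will agree. The 4/17 contrast arises at a result the count rule already fails. The comparison with section 10.4.3 is weak evidence of intent: that sentence speaks of several cohorts although section 2.3.2 lists one, so it may be carried-over wording (an inference). Section 10.4.6 is consistent with a futility-only stop.

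**Conclusion.** No change is needed. Section 10.4.2 leaves out the interval method, and the secondary endpoint has one more level than the primary, but the plan as written still gives a sound result. The count rule decides, with type I error 0.094 and power 0.904, and neither depends on the interval. If the interval is the ordinary exact one, 95% coverage holds at 95.6% or more for true rates of 20% to 50%, and the stop shifts the limits by at most 0.7 point at any passing result. An 80% interval would be an optional extra, and its agreement with the rule at the cut would depend on the method and on the final denominator.

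This rests on stage sizes of 10 and 7 and on the analyst using an exact interval; the coverage figure does not carry over to Wilson. It does not touch the separate question of why the objective is to exceed 25% while the design tests against 20%.
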